3.4.3 Other Endpoints

Observed results, change from baseline, and percent change from baseline for eGFR (estimated by the creatinine-cystatin C method) will be summarized by visit using descriptive statistics. The number of days of hospitalizations and re-hospitalizations for any reason will be summarized.

Number and percentage for patients will be presented for following endpoints.

- Patients with biopsy-proven acute allograft rejection. The results will be provided by severity (adjudicated Banff classification)
- Patients using immunosuppressive agents, including specific immunosuppressive agents used. The doses, and any changes in dose will be listed.
- Patients with kidney injury requiring hemodialysis
- Patients with hospitalizations/re-hospitalizations for any reason

The use of antiviral therapies will be listed as concomitant medications but not summarized.

The analyses for all the efficacy endpoints are summarized in Table 1:

Table 1: Efficacy Endpoints Summary and Statistical Analysis

| Type of Endpoint | Summary Table | |
|---|------------------------|---------------------|
| | Population | Variables[*]/Method |
| Continuous | | |
| • BK viral load | Observed/Chg/Pchg | |
| • eGFR by MDRD | Observed/Chg/Pchg | |
| • eGFR by Creatinine-cystatin C | Observed/Chg/Pchg | |
| Time to event [#] | | |
| • Time to BKV resolution | Kaplan-Meier | |
| • Duration of BKV remission | Kaplan-Meier | |
| Category | | |
| • BKV resolution | Categories: Yes/No | |
| • 1 Log10 reduction of BK viral post infusion | Categories: Yes/No | |
| • Patients with screening BK viremia <10,000 copies/mL develop BK viremia ≥10,000 copies/mL | Categories: Yes/No | |
| • Donor specific anti-HLA antibodies | Categories: Yes/No | |
| • eGFR >20 mL/min/1.73m ² | Categories: Yes/No | |
| • New viral infection | Categories: Yes/No | |
| • Immunosuppression reduction | Categories: Yes/No | |
| • Immunosuppressive agents | Categories: agent type | |
| • Biopsy-proven acute allograft rejection | Categories: severity | |
| • Kidney injury requiring hemodialysis | Categories: Yes/No | |
| Category and continuous | | |
| • Hospitalizations/re-hospitalizations | Yes/No; Duration | |

N/A = Not Applicable.

[*] Chg = Change from Baseline; Pchg = Percent Change from Baseline.

[\$] Line plot will be generated.

[#] Kaplan-Meier plot will be generated for each endpoint.

[**] Ratio is defined as unique clonotype donor DNA/patient DNA*100.

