1.3 Schedule of Activities

Table 1 Period 1 (Weeks -2 to 12)

At the discretion of the Investigator, and with the exception of Weeks 8 and 12 (which must be conducted at the site), study visits for patients who have undetectable BK plasma viral load at 2 or more consecutive assessments at least 2 weeks apart after 3 doses may be conducted by a Sponsor-approved home health vendor in conjunction with a Sponsor-approved telehealth provider. These visits may be conducted via video or telephone call.

Study Week	Weeks -2 to -1	Day 1	Week 1	Week 2	Week 4	Week 6	Week 8	Week 10	Week 12
Study Day	-14 to -1	1 ^[1]	8	15	29	43	57	71	85
Visit Window (Days)	NA	NA	±2	±3	±3	±3	±3	±3	±3
Study Procedures									
Informed consent ^[2]	X								
I/E criteria	X	X							
Demographics	X								
Medical history	X								
Prior & concomitant medications	X	X	X	X	X	X	X	X	X
Adverse events ^[3]	X	X	X	X	X	X	X	X	X
Complete physical examination ^[4]	X	X							X
Targeted physical examination ^[4]			X	X	X	X	X	X	
Weight and height ^[5]	X	X			X		X		X
Vital signs ^[6]	X	X	X	X	X	X	X	X	X
12-lead ECG ^[7]	X	X ^[7]		X ^[7]					
Documentation of HLA typing ^[8]	X								
Clinical labs ^[9]	X	X		X	X	X	X	X	X
Testing for HIV, HCV, and HBV ^[22]	X								
BKV plasma viral load ^[10,11]	X	X		X	X	X	X	X	X
Urine for biomarker ^[12]		X			X		X		X
AdV, CMV, JCV, HHV-6 plasma, and EBV viral load ^[10]		X			X		X		X
Pregnancy test	X ^[13]	X ^[14]			X ^[14]		X ^[14]		X ^[14]
FSH ^[15]	X								
Randomization ^[16]		X							
Provide patient cards		X							

Study Week	Weeks -2 to -1	Day 1	Week 1	Week 2	Week 4	Week 6	Week 8	Week 10	Week 12
Study Day	-14 to -1	1 ^[1]	8	15	29	43	57	71	85
Visit Window (Days)	NA	NA	±2	±3	±3	±3	±3	±3	±3
Study treatment administration ^[17]		X	X	X	X	X	X	X	X
Post infusion monitoring ^[18]		X	X	X	X	X	X	X	X
Banked PBMCs for virus specific immunity ^[19]	X			X	X	X	X		X
Blood for donor DNA ^[20]					X				X
Kidney biopsy pathologic specimens for review (if clinically indicated) ^[23]	X	X	X	X	X	X	X	X	X
Donor-specific antibodies ^[24]		X							X

1. Unless noted otherwise, the Day 1 procedures must be performed within 96 hours of randomization and prior to study treatment administration.
2. Prior to conducting any study-related activities, written informed consent to participate in the study must be provided by the patient.
3. Adverse events will be monitored and documented from randomization through Week 24 in all patients.

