6.8.1 Excluded Medications and/or Procedures

All patients may receive available supportive therapy with approved treatments, but initiation of therapy *for the attempted treatment of BK virus infection* with sirolimus, everolimus, cidofovir, brincidofovir, fluoroquinolones (eg, ciprofloxacin), intravenous immunoglobulin (IVIG) or leflunomide during the first 12 weeks after randomization is prohibited.

Receipt of other investigational antiviral treatments (eg, anti-BK virus monoclonal antibodies) within 28 days or 5 half-lives (whichever is longer) prior to randomization and throughout the duration of the study is prohibited.

T cell ablative therapies such as antithymocyte globulin, alemtuzumab (Campath-1H), or other immunosuppressive T cell-targeted monoclonal antibodies are prohibited during the study. Daily doses of corticosteroids exceeding 0.5 mg/kg prednisone (or equivalent) are also prohibited during the study.

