2.3.4 Other Endpoints

The other endpoints include the following:

- Frequency and severity (adjudicated Banff classification) of biopsy-proven acute allograft rejection in recipients of PSL versus placebo.
- Number of patients in the investigational arms with polyomavirus haufen in the urine as compared to the placebo arm.
- Quantification of IFN- γ (+) T cells specific for BK virus in patients in the investigational arms as compared to the placebo arm.
- Levels of (virus-specific T cell) donor T cell deoxyribonucleic acid (DNA) as compared to patient T cell DNA in peripheral blood.
- Time to resolution of non-BK target viral infections (i.e., associated signs, symptoms, and presence/absence of HHV-6, EBV, JCV, and/or AdV viremia) present at the time of randomization.
- Use of immunosuppressive agents, including specific immunosuppressive agents used, doses, and any changes in dose.
- Number of hospitalizations/re-hospitalizations for any reason and number of days.
- Incidence and duration of use of any other antiviral therapies during the study.
- Time to death (from any cause) from the time of randomization.
- Number of patients with kidney injury requiring hemodialysis.
- Rate of decline of BK viremia in recipients of PSL using different dosing intervals versus that in patients receiving placebo.

- Assessment of renal function (eGFR estimated by the creatinine-cystatin C method reported by central lab).

The biomarker data, including IFN- γ (+) T cells specific for BK virus, polyomavirus haufen in the urine, and T cell receptor sequencing data will not be analyzed in this SAP but reported separately.

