3.4.2 Exploratory Efficacy Endpoints

Observed results, change from Baseline, and percent change from baseline for eGFR estimated by MDRD and creatinine will be summarized by visit using descriptive statistics.

Donor specific anti-HLA antibodies (DSA) (yes/no) will be summarized by visit using descriptive statistics.

Resolution of viremia will be generally defined as achieving a post-baseline viral load measure below the lower limit of quantification (<LLOQ) for that viral assay. The number of patients with resolution for each virus (BKV, CMV, EBV, AdV, JCV, and/or HHV-6) will be summarized by visit and at any visits. In addition, the proportion of patients reaching at least 1 log10 reduction or <LLOQ in BK viral load post infusion will be summarized by visit and at any visits.

LLOQ values for the viruses of interest are:

BKV Viral Load (Copy/mL): LLOQ = 156

Non-BK Target Viruses:

ADV Viral Load (Copy/mL): LLOQ = 32

CMV Viral Load (Copy/mL): LLOQ = 65.6

EBV Viral Load (Copy/mL): LLOQ = 37

HHV-6 Human Herpesvirus 6 (Copy/mL): LLOQ = 110

JCV JC Virus (IU/mL): LLOQ = 76

Time-to-event endpoints will be summarized using the Kaplan-Meier method. Number of patients with events and number of patients censored and reason of censoring will be presented along with estimate for the median time (days) and its 95% CI. Time-to-event will be presented using Kaplan-Meier plots.

Time to resolution of BK viremia will be calculated as starting at randomization for patients with detectable virus and ending at the first undetectable viral load (i.e., <LLOQ). Patients who discontinued from the study early or deceased before they are observed to have achieved resolution will be censored at the last assessment date for this endpoint.

For patients who reach the resolution of BK viremia, time to reappearance of BK viremia (duration of viral remission) will be calculated as starting at the first assessment with undetectable viral load and ending at the first detectable viral load (confirmed with 2 consecutive measures at least 8 days apart, or end of study if only one measure is available). Patients not demonstrating the reappearance of viremia would be censored on the date of the latest assessment for this endpoint. Patients who discontinued from the study early or deceased before they are observed to have will be censored at the last assessment date for this endpoint.

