APPENDIX B: ANALYSIS VISIT WINDOWS

Table 1. Analysis Visit Windows for Physical Exams and Vital Signs

| Nominal Visit | Nominal Study Day | Visit Window Study Day | |
|----------------|-------------------|------------------------|-------------|
| | | Lower Limit | Upper Limit |
| Day 1/Baseline | 1 | 1 | 1 |
| Week 1 | 8 | 2 | 11 |
| Week 2 | 15 | 12 | 22 |
| Week 4 | 29 | 23 | 36 |
| Week 6 | 43 | 37 | 50 |
| Week 8 | 57 | 51 | 64 |
| Week 10 | 71 | 65 | 78 |
| Week 12 | 85 | 79 | 92 |
| Week 14 | 99 | 93 | 106 |
| Week 16 | 113 | 107 | 120 |
| Week 18 | 127 | 121 | 134 |
| Week 20 | 141 | 135 | 148 |
| Week 22 | 155 | 149 | 162 |
| Week 24 | 169 | >162 | |

Table 2. Analysis Visit Windows for BK Viral Loads

| Nominal Visit | Nominal Study Day | Visit Window Study Day | |
|----------------|-------------------|------------------------|-------------|
| | | Lower Limit | Upper Limit |
| Day 1/Baseline | 1 | 1 | 1 |
| Week 2 | 15 | 2 | 22 |
| Week 4 | 29 | 23 | 36 |
| Week 6 | 43 | 37 | 50 |
| Week 8 | 57 | 51 | 64 |
| Week 10 | 71 | 65 | 78 |
| Week 12 | 85 | 79 | 92 |

| | | | |
|---------|-----|------|-----|
| Week 14 | 99 | 93 | 106 |
| Week 16 | 113 | 107 | 120 |
| Week 18 | 127 | 121 | 134 |
| Week 20 | 141 | 135 | 148 |
| Week 22 | 155 | 149 | 162 |
| Week 24 | 169 | >162 | |

Table 3. Analysis Visit Windows for Clinical labs

| Nominal Visit | Nominal Study Day | Visit Window Study Day | |
|----------------|-------------------|------------------------|-------------|
| | | Lower Limit | Upper Limit |
| Day 1/Baseline | 1 | 1 | 1 |
| Week 2 | 15 | 2 | 22 |
| Week 4 | 29 | 23 | 36 |
| Week 6 | 43 | 37 | 50 |
| Week 8 | 57 | 51 | 64 |
| Week 10 | 71 | 65 | 78 |
| Week 12 | 85 | 79 | 99 |
| Week 16 | 113 | 100 | 127 |
| Week 20 | 141 | 128 | 155 |
| Week 24 | 169 | >155 | |

Table 4. Analysis Visit Windows for Non BK viruses

| Nominal Visit | Nominal Study Day | Visit Window Study Day | |
|----------------|-------------------|------------------------|-------------|
| | | Lower Limit | Upper Limit |
| Day 1/Baseline | 1 | 1 | 1 |
| Week 4 | 29 | 2 | 43 |
| Week 8 | 57 | 44 | 71 |
| Week 12 | 85 | 72 | 99 |
| Week 16 | 113 | 100 | 127 |

| | | | |
|---------|-----|------|-----|
| Week 20 | 141 | 128 | 155 |
| Week 24 | 169 | >155 | |

Table 5. Analysis Visit Windows for ECG data

| Nominal Visit | Nominal Study Day | Visit Window Study Day | |
|----------------|-------------------|------------------------|-------------|
| | | Lower Limit | Upper Limit |

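### The bar on starting BK-directed drugs ends 12 weeks after randomization, but BK results run to Week 24 with no analysis of such starts and no summary of their timing or duration

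*SAP*

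**What the plan says.** **The restriction.** Protocol 6.8.1 names sirolimus, everolimus, cidofovir, brincidofovir, fluoroquinolones, IVIG and leflunomide. Starting one of them to treat BK infection "during the first 12 weeks after randomization is prohibited". The rule covers starting only, and the exclusion criteria in Protocol 5.2 do not name these drugs. Other investigational antivirals are handled differently: their receipt shortly before randomization "and throughout the duration of the study is prohibited".

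**The BK outcomes.** SAP Appendix B sets BK viral load windows to Week 24. SAP 3.4.1 summarizes BK load by visit. SAP 3.4.2 counts resolution and the 1 log10 response both by visit and at any visit, and adds time to resolution and duration of remission. Patients without an event are censored at their last assessment. SAP 3.1.5 uses data as observed. The only BK sensitivity analysis (SAP 3.4.2) carries the last observation forward for missing values.

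**Reporting of antiviral use.** SAP 2.3.4 lists as an endpoint: "Incidence and duration of use of any other antiviral therapies during the study". SAP 3.4.3 then states: "The use of antiviral therapies will be listed as concomitant medications but not summarized", and SAP Table 1 omits the endpoint. SAP 3.3.5 nevertheless plans counts of all concomitant medications by ATC class and preferred term. SAP 3.3.6 and 3.4.3 add counts by immunosuppressive agent.

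**The concern.** A patient who is still viremic at Week 12 may be given a BK-directed drug in follow-up. If that patient's load later falls below the limit of quantification, the SAP counts a resolution for the assigned arm, and time to resolution ends there. Nothing planned separates this patient from one who cleared without added treatment.

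The results at stake are BK load in Weeks 14 to 24, any-visit resolution and 1 log10 response, time to resolution, duration of remission and late AUC. These are the results a reader would use to judge whether an effect lasts after infusions stop. A summary of the listed antiviral-use endpoint is what would show how much added treatment each arm received, and the SAP declines to produce it.

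**Working it through.** **Visits after the restriction.** Post-baseline BK visits in SAP Appendix B are Weeks 2, 4, 6, 8, 10, 12, 14, 16, 18, 20, 22 and 24, which is 12. Weeks 14, 16, 18, 20, 22 and 24 come after Week 12, so 6 of 12 are exposed to permitted starts.

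**What the planned tables can show.**
- Concomitant medications (SAP 3.3.5): number and percentage by ATC class and preferred term. SAP 3.1.4 presents summaries by treatment group and stratum.
- Immunosuppressive agents (SAP 3.4.3): number and percentage by agent, which would cover sirolimus and everolimus.
- Immunosuppression reduction (SAP 3.4.2): detects a dose cut of at least 50% from baseline and leaves out leflunomide and IVIG, so it cannot detect a start.
- None of these gives start relative to Week 12, duration or BK indication. Protocol 6.8 collects indication and dates, so these could be derived.

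**Weight of one patient.** With 20 patients per arm (Protocol 9.2; 3 × 20 = 60), one placebo patient is 1/20 = 5 points and one patient in the pooled PSL arms is 1/40 = 2.5 points.

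**Illustration of size.** The documents give no rates for resolution, drug starts or clearance, so every rate here is an assumption. Let r be the drug-free any-visit resolution rate, s the share of unresolved patients who start a drug after Week 12, and c the share of starters who clear because of it. Then

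observed rate = r + (1 − r) × s × c.

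Take r = 0.30 for placebo and 0.50 for pooled PSL, a 20-point difference.

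| s placebo | s PSL | c | Placebo observed | PSL observed | Difference (points) |
|---|---|---|---|---|---|
| any | any | 0 | 0.300 | 0.500 | 20.0 |
| 0.10 | 0.10 | 0.50 | 0.335 | 0.525 | 19.0 |
| 0.40 | 0.10 | 0.10 | 0.328 | 0.505 | 17.7 |
| 0.40 | 0.10 | 0.30 | 0.384 | 0.515 | 13.1 |
| 0.40 | 0.10 | 0.50 | 0.440 | 0.525 | 8.5 |
| 0.10 | 0.40 | 0.50 | 0.335 | 0.600 | 26.5 |

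For the fifth row: placebo 0.30 + 0.70 × 0.40 × 0.50 = 0.440; PSL 0.50 + 0.50 × 0.10 × 0.50 = 0.525. The difference moves little when start rates are equal. It shrinks if placebo patients start more often and grows if PSL patients do.

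**The two clocks.** The restriction counts from randomization (84 days). SAP 3.1.1 counts study day from first dose, so Day 85 is first dose + 84 days. The Schedule of Activities puts randomization on Day 1, so the nominal gap is 0 days. Footnote 1 says that "the Day 1 procedures must be performed within 96 hours of randomization and prior to study treatment administration". If that allows dosing 4 days after randomization and Week 12 falls at +3 days, the sample is at 4 + 84 + 3 = 91 days, 7 days after the restriction ends. The SAP's Week 12 BK window closes on Day 92 (first dose + 91 days), so even with same-day dosing a sample in that window can be 91 − 84 = 7 days past it.

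**The case against.** Four points have force.

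- **The drugs may not work.** Protocol 4.2 calls leflunomide, cidofovir, intravenous immunoglobulin and levofloxacin ineffective, and says that only immunosuppression reduction has lowered BK load. A reader might infer that clearance caused by these drugs will be credited to placebo and will hide a lasting PSL effect. The documents do not support that: no passage says a named drug clears BK, and none gives start rates by arm. What remains is that Protocol 4.2 also reports continued use of such drugs, and the amendment rationale gives confounding as the reason for barring sirolimus and everolimus starts during treatment.
- **Some of the information is planned.** A reader might infer that drug use by arm will be invisible. That is not so, because counts by drug and arm remain, together with by-patient listings. The gap is timing, duration and indication in a summary, plus the conflict between SAP 3.3.5 and 3.4.3.
- **The endpoint was optional in the protocol.** Protocol 9.4.6 says that the endpoints in its list may be analyzed, so the SAP does not break a protocol commitment. The inconsistency lies within the SAP, between 2.3.4 and 3.4.3.
- **As-observed analysis is legitimate.** Counting outcomes whatever is added later is a recognized treatment-policy choice. The SAP, however, neither says that it is making this choice nor plans a supporting analysis.

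The clock difference might also be read as placing BK drug starts before the Week 12 sample as a matter of course. The 7-day gap at the scheduled visit needs both the longest dosing lag and the latest visit day, and the 7 days in the SAP window needs a sample on its last day. No effect of a drug started that close to the sample is shown.

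**Conclusion.** The gap is real but limited. Half of the post-baseline BK visits follow the end of the restriction, no analysis addresses permitted starts, and the SAP lists an antiviral-use endpoint that it then declines to summarize. Any effect on the comparison requires that use differs by arm and that the drugs change BK load. Neither is known, so neither the direction nor the size can be stated. The 8.5 to 26.5 point range only shows how far an assumed 20-point difference could move under the rates tried.

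The primary endpoint is safety, Protocol 9.1 plans no formal hypothesis testing, and the SAP efficacy summaries are descriptive. Week 8 resolution and nominal by-visit results through Week 12 are not exposed to permitted starts. The change is still worth making: it is cheap, and it shows whether the Week 14 to 24 results reflect assigned treatment alone. The clock difference is minor.

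**What to change.** 1. In SAP 3.4.3, replace the sentence that declines a summary with a by-arm table of patients using any drug named in Protocol 6.8.1 for BK: ongoing at baseline, started before Week 12, or started after Week 12, with start week and duration. Add it to SAP Table 1 and bring 2.3.4, 3.3.5 and 3.4.3 into agreement.
2. Keep the as-observed analysis as the main one, and state that it counts BK outcomes regardless of such starts.
3. Add one sensitivity analysis of time to resolution and any-visit resolution in which a patient who starts such a drug before clearing counts as not resolved from then on.
4. Reconcile the restriction period in Protocol 6.8.1 (from randomization) with study day in the SAP (from first dose), so that it is clear whether the Week 12 sample lies inside the restricted period.

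The cost is SAP wording, one table and one sensitivity analysis. Indication and dates are already collected under Protocol 6.8, and the main results do not change. The sensitivity analysis answers a different question from the main one and should be labeled as supporting.

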3.5 Safety Analyses

Safety data will be summarized by treatment group (i.e., PSL, Placebo and Overall). Safety summary tables will be generated for actual treatment received, based on the Safety Population. The primary objective of the study is to assess the safety and tolerability of PSL in kidney transplant recipients based on TEAEs and changes in vital signs, physical examinations, clinical laboratory assessments, and ECGs. Categorical endpoints will be summarized using the number and percentage of patients within each category. Continuous endpoints will be summarized descriptively with summary statistics (number, mean, standard deviation, standard error, median, first quartile, third quartile, minimum, and maximum).

